Study Question:	What is the utility of the combination of the novel QuantiFERON-Monitor (QFM) and donor-specific cell free DNA (dscfDNA) blood tests in monitoring and managing immunosuppression post liver transplantation (LT)?		
Study Objectives:	To determine the utility of the combined QFM and DNA (QFM- dscfDNA) tests in monitoring and managing immunosuppression post LT.		
Primary Objectives:	To examine if the QFM-DNA tests can be used to accurately diagnose acute rejection and infective complications after LT.		
Secondary Objectives	To examine if the QFM-DNA tests can be used to predict acute rejection or infective complications, monitor treatment responses, and improve healthcare resource utilisation.		
Inclusion Criteria:	 Age 18 years and above Undergoing LT at Austin Health Can provide written informed consent 		
Exclusion Criteria:	 Aged under 18 years Undergoing multi-organ transplantation Unable to provide written informed consent at any stage 		
Number of Planned Subjects:	210		
Investigational product:	Nil		
Safety considerations:	Participants will be required to have serial additional blood sampling, performed when blood tests for the standard of care for LT occur wherever possible. They may be subjected to mild physical or psychological distress during venepuncture. There will be no deviation from standard of care treatment.		
Statistical Methods:	Receiver-operator characteristics analysis.Logistic regression analysis.		
Subgroups:	Nil		

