8. STATISTICAL METHODS

a. SAMPLE SIZE ESTIMATION & JUSTIFICATION

We propose enrolling a total of 210 LT recipients during a three-year recruitment period. This timeframe is anticipated to be easily feasible as the LTU performs an average of 75 adult LTs each year. Most recipients will fulfil the trial's inclusion and exclusion criteria; hence non-eligibility (including refusal of informed consent) is anticipated to be low (about 5%). In addition, lost-to-follow-up (including death) is anticipated to be very low (about 1-2%) during the 12-month follow-up².

In preliminary research from Austin Health¹⁶, 31% of the recipients experienced tBPAR as the first event after LT while 41% experienced a 'probable'/'definite' infective complication as the first event after LT, both within a 12-month follow-up period. To be conservative, we assume 30% of our recruited recipients will experience at least one tBPAR and 40% at least one infective complication. The sample size of 210 LT recipients will allow us to estimate a fair AUC of 0.7 using a two-sided 95% confidence interval with precision \pm 0.081 for tBPAR and \pm 0.075 for infection and a good AUC of 0.8 with a precision of \pm 0.075 for tBPAR and \pm 0.069 for infection^{21,22}.

b. POWER CALCULATIONS

This sample size will provide a power of 99.7% to show that the combination has any ability to discriminate between those with and without tBPAR and 99.9% power between those with and without infection, (null hypothesis AUC of 0.5), assuming that we observe a fair AUC of 0.7 with 5% alpha²¹.

c. STATISTICAL METHODS TO BE UNDERTAKEN

All participants will be included in the final analyses. Diagnostic performance of QFM and dscfDNA combined for the first tBPAR and the first 'probable'/'definite' infective complication will be assessed by evaluation of sensitivity, specificity, the positive and negative predictive value and diagnostic accuracy. Diagnostic accuracy will be evaluated by determining the AUC and two-sided 95% confidence interval. Given that QFM and dscfDNA outcomes are measured repeatedly over 12 months, we will initially summarise these outcomes across time-points using the average, nadir, standard deviation and slope and fit a logistic regression model.

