Next, we will look at moving average, moving standard deviation, and change of slope and fit a mixed logistic regression model. Finally, a joint model for longitudinal tBPAR, respectively longitudinal infective complications, and QFM, dsfDNA and LFT outcomes will be explored. This model will allow investigation of the temporal dynamics of rejection and infection, and evaluate the usefulness of QFM and dscfDNA for monitoring purposes²³.

We will compare the AUC of using QFM alone or dscfDNA alone versus the combination. An optimal threshold of QFM and dscfDNA in identifying recipients at risk of tBPAR or infection will be established. A detailed statistical analysis plan will be prepared prior to locking of the

database.

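### Section 8.c judges what the second test adds by comparing AUCs of what are probably nested models; a likelihood-ratio test of the added terms is a better-calibrated and more powerful basis

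*Protocol*

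**What the plan says.** The synopsis puts the study question as "What is the utility of the combination of the novel QuantiFERON-Monitor (QFM) and donor-specific cell free DNA (dscfDNA) blood tests" in monitoring and managing immunosuppression. Section 8.c contains the comparison of the pair with its components: "We will compare the AUC of using QFM alone or dscfDNA alone versus the combination". It names no test, interval method or validation scheme for that difference, and it defers detail to a statistical analysis plan to be written before database lock.

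The same section says how repeated measurements become predictors: "we will initially summarise these outcomes across time-points using the average, nadir, standard deviation and slope and fit a logistic regression model". It also says "All participants will be included in the final analyses".

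Sections 8.a and 8.b size the study for one AUC at a time: the width of its interval, and its power against 0.5. Neither addresses a difference between two AUCs. The primary endpoints in section 4.c set QFM and dscfDNA, singly and together, against LFTs.

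**The concern.** A logistic model holding both markers' summaries contains each single-marker model as a special case. The null of interest is that the second marker's coefficients are all zero. Under it the two fitted scores converge on the same score. The AUC difference, computed on the recipients used for fitting, is then skewed and mostly positive. A standard paired test treats the two scores as distinct and fixed, with a difference that is normal around zero. That null distribution does not apply here.

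The answer to whether the second assay is worth adding therefore depends on how the AUC difference is handled. Read by eye, the combination nearly always looks better. With some tests a real but modest gain is often missed. With one common bootstrap and several summaries, noise is often declared a gain. Section 3.b says positive findings would lead to a randomised multi-centre trial, so the answer bears on whether that trial carries both assays.

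**Working it through.** **Inputs from the protocol.** N = 210. Event rates are from section 8.a: "we assume 30% of our recruited recipients will experience at least one tBPAR and 40% at least one infective complication". That gives 210 × 0.30 = 63 tBPAR cases and 147 non-cases, and 210 × 0.40 = 84 infection cases and 126 non-cases. The reference AUC is 0.70 and alpha is 5%. Section 8.b does not state sidedness; I used two-sided.

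**Inputs I assumed.** The protocol gives no marker strengths or correlations. I took normal, independent markers, a first marker of AUC 0.70, and an added marker of AUC 0.50 (no value), 0.62 or 0.65. Each marker has either one summary or four, with one of the four informative. Models are fitted and evaluated on the same recipients.

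**Step 1: the plan's own figures reproduce.** The binormal variance of one AUC is V = 0.0099·exp(−a²/2)·[(5a² + 8) + (a² + 8)/k], with a = 1.414·z(AUC), k = non-cases/cases and SE = √(V/cases).
- tBPAR, AUC 0.7: a² = 0.550, k = 2.333, V = 0.1084, SE = 0.0415, half-width 1.96 × SE = 0.081.
- Infection, AUC 0.7: k = 1.5, V = 0.1237, SE = 0.0384, half-width 0.075.
- AUC 0.8: half-widths 0.075 and 0.069.
- Power against 0.5 is Φ((0.2 − 1.96·SE₀)/SE₁). For tBPAR, SE₀ = 0.0424, giving Φ(2.82) = 99.76%; a Hanley-McNeil variance gives 99.72%. For infection, SE₀ = 0.0396, giving Φ(3.19) = 99.93%.

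These match the stated values, but they describe a single AUC, not added value.

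**Step 2: the true gains in play.** For independent binormal markers, the combined AUC is Φ(√(z₁² + z₂²)), with z₁ = z(0.70) = 0.524.
- Added 0.62: z₂ = 0.305, Φ(√(0.275 + 0.093)) = Φ(0.607) = 0.728, a gain of 0.028.
- Added 0.65: z₂ = 0.385, Φ(√(0.275 + 0.148)) = Φ(0.651) = 0.742, a gain of 0.042.

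**Step 3: paired DeLong test against the likelihood-ratio test.** Ranges cover tBPAR (63/147) and infection (84/126).

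| Added marker | Summaries per marker | DeLong rejects | Likelihood ratio rejects |
|---|---|---|---|
| No value | 1 | about 0.1% | about 4-6% |
| No value | 4 | about 2% | about 6% |
| AUC 0.62 | 1 | 16-18% | 78-82% |
| AUC 0.62 | 4 | 26-32% | 56-64% |
| AUC 0.65 | 1 | 34-42% | 93-96% |
| AUC 0.65 | 4 | 47-54% | 80-85% |

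A repeat run of 2,000 datasets per row and endpoint agreed with these within simulation error.

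**Step 4: comparison by eye.** With no true gain, the combination's apparent AUC is higher in about 74% of datasets with one summary and 96% with four. The mean apparent rise is about 0.004 and 0.015.

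**Step 5: bootstrap with refitting, no true gain** (200-300 datasets, 200 resamples each, so about ±7 points near 50%).
- Percentile interval: false gains in 0.7-2.3% with one added summary, but about 43-54% with four.
- z-test with a bootstrap standard error: 0-4%, which is conservative.

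**Step 6: sensitivity.** With summaries correlated 0.3 within each marker and four summaries, DeLong null rejection is 1.8-2.0%. At a true gain near 0.036, power is 40-44% against 72-75%; near 0.050 it is 60-67% against 88-91%. With one summary and a gain near 0.050 it is 45-51% against 96-98%.

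**The case against.** The strongest reply is that the protocol commits to none of the tests simulated above. It says only that AUCs will be compared, and it promises an analysis plan, where the method for an AUC difference would ordinarily be fixed. That stands: neither harm follows from the protocol's words alone. What the protocol does fix is the yardstick, and no usual test of that yardstick tried here has both correct size and good power.

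Nesting is also inferred. Section 8.c does not say how the single-test and combined scores are built, and a single-test AUC could come from a raw marker. This stands as a condition on the point. Logistic models on summaries in all participants are nevertheless the natural reading.

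Three stronger readings are tempting, and the documents do not support them:
- **A real gain will mostly be missed.** With a DeLong test this holds for true gains up to about 0.035-0.04. Near 0.05 its power is 45-67%. The gains at issue are small beside the stated precision of ±0.069 to ±0.081 for one AUC.
- **A bootstrap will declare false gains.** This needs percentile intervals and several added summaries. The largest power loss (one summary) and the high false-gain rate (four) belong to different settings and should not be cited together.
- **The primary analysis is compromised.** The comparison with LFTs is not nested unless LFTs enter the same model.

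Finally, AUC is the study's declared accuracy measure, and a likelihood-ratio test can be significant for a very small gain. That is a reason to keep an interval for the AUC difference beside the test, not to drop inference on it.

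**Conclusion.** The point holds as an inexpensive improvement to section 8.c, not as an error in a stated figure. If the combined and single-test scores come from the planned logistic models, testing added value through the AUC difference is badly calibrated at this sample size. Against a likelihood-ratio test, a paired DeLong test gives up roughly 55-65 points of power with one summary per marker and about 30 points with the four that the protocol lists, for true gains of about 0.03-0.04. A reader might infer that the error has a known direction; it does not, because that depends on a method the protocol leaves open. The power figures rest on assumed normal, independent markers, a first marker of AUC 0.70 and fixed case counts. Other strengths or correlations would change the figures but would not remove the nesting.

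**What to change.** In section 8.c, state that the added value of the combination over QFM alone and over dscfDNA alone will be assessed by a joint likelihood-ratio test of all the added marker's terms in the logistic model, two-sided 5%, separately for tBPAR and infection. State that the AUC difference will be reported beside it as an optimism-corrected estimate (bootstrap or cross-validated) with an interval, as the measure of size. Apply the same rule if LFTs enter a model together with the new tests. A direct AUC comparison remains suitable for non-nested scores such as QFM alone against dscfDNA alone.

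The cost is wording in the protocol and the analysis plan. The models are already planned, and no patients, samples or assays are added. The small downside is that a significant likelihood-ratio test does not show a clinically large AUC gain, so the two results must be read together.

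### Section 8.b claims power at 5% alpha for a fixed score, but 8.c fits the QFM-dscfDNA combination and its threshold on the same 210 participants and states no internal validation

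*Protocol*

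**What the plan says.** Section 8.a of the protocol sets the size: "We propose enrolling a total of 210 LT recipients during a three-year recruitment period". On event rates, "we assume 30% of our recruited recipients will experience at least one tBPAR and 40% at least one infective complication". It gives 95% confidence interval half-widths of 0.081 (tBPAR) and 0.075 (infection) at an AUC of 0.7, and 0.075 and 0.069 at an AUC of 0.8.

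Section 8.b then claims a "power of 99.7% to show that the combination has any ability to discriminate between those with and without tBPAR", and 99.9% for infection, against a null AUC of 0.5 with 5% alpha at an AUC of 0.7.

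Section 8.c describes how the combination arises. The repeated QFM and dscfDNA values are reduced to average, nadir, standard deviation and slope and entered in a logistic regression. A mixed logistic model on moving summaries follows, and then a joint model is explored. Diagnostic accuracy is the AUC with a two-sided 95% confidence interval, reported with sensitivity, specificity, PPV and NPV. The section adds "We will compare the AUC of using QFM alone or dscfDNA alone versus the combination" and "An optimal threshold of QFM and dscfDNA in identifying recipients at risk of tBPAR or infection will be established". All participants enter the final analyses. No previously fixed score or cut-off, split sample, cross-validation, bootstrap or optimism correction is mentioned. A detailed SAP is promised before database lock; it is not available here.

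**The concern.** The calculation in 8.b belongs to a single score whose weights are known before the data are seen. The combination in 8.c is not such a score, because its weights, and possibly the choice of summaries, come from the participants on whom it is judged. A regression score chosen to separate cases from non-cases has an in-sample AUC centred above 0.5 even when both markers are noise. An ordinary confidence interval around that AUC takes no account of the fitting. The 5% alpha printed in 8.b would then not apply to the analysis in 8.c.

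A cut-off chosen as optimal in a data set also performs better there than in new patients, which affects sensitivity, specificity, PPV and NPV.

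The AUC of the markers alone and in combination is the primary endpoint (4.c), and the introduction (3.b) says that positive findings will lead to a randomised multi-centre trial. A claim of discrimination from noise, or overstated accuracy, would therefore have consequences.

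**Working it through.** **Inputs.** From 8.a: N = 210; tBPAR 0.30 × 210 = 63 cases against 147; infection 0.40 × 210 = 84 against 126. From 8.b: null AUC 0.5, AUC 0.7, alpha 5% (taken as two-sided). From 8.c: 4 summaries × 2 markers = 8 candidate predictors in the first step.

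**Step 1: reproduce the plan's figures.** Obuchowski's binormal variance, with A = 1.414 × z(AUC) and R = non-cases/cases:

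Var = 0.0099 × exp(−A²/2) × [(5A² + 8) + (A² + 8)/R] / cases

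- tBPAR, AUC 0.7: A² = 0.55, R = 2.33, SE = 0.0415; half-width 1.96 × 0.0415 = 0.081.
- Infection, AUC 0.7: R = 1.5, SE = 0.0384; half-width 0.075.
- AUC 0.8: SE 0.0385 and 0.0352; half-widths 0.075 and 0.069.

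All four match. Power = Φ[(0.2 − 1.96 × SE₀)/SE₁]:

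- tBPAR: (0.2 − 1.96 × 0.0424)/0.0415 = 2.82, or 99.76%. The Hanley-McNeil SEs give 99.72%.
- Infection: (0.2 − 1.96 × 0.0396)/0.0384 = 3.19, or 99.93%.

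Both agree with the stated figures. Neither formula contains a term for fitting the score.

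**Step 2: the analysis as written, with no true signal.** Monte Carlo: normal noise predictors, logistic model fitted to all 210, AUC of the fitted score on the same data, DeLong 95% interval.

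| Predictors fitted | Mean apparent AUC | Interval excludes 0.5 |
|---|---|---|
| 1 | about 0.53 | about 4-5% |
| 2 (one summary per marker) | 0.55 | about 15% |
| 4 | about 0.58 | about 41-44% |
| 8 (all first-step summaries) | 0.61-0.62 | about 85-86% |

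The results are much the same for tBPAR and infection. If instead the best of the four summaries per marker is picked (16 pairs, assumed correlation 0.5), the figure is about 54-55%.

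**Step 3: a true AUC of 0.7 carried by one predictor.**

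- Two predictors: apparent AUC 0.704-0.705, about 0.695 in new data; excess about 0.01.
- Eight predictors: apparent 0.725-0.728, 0.674-0.676 in new data; excess about 0.05. That is roughly two-thirds of the stated half-width (0.054/0.081 = 0.67; 0.049/0.075 = 0.65).

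**Step 4: the threshold.** For a single fixed score with AUC 0.7, the Youden index (sensitivity + specificity − 1) at the best in-sample cut-off averages 0.34. The same cut-off gives about 0.27 in new data.

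**Step 5: does a valid method cost power?**

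- The likelihood-ratio test of the fitted model rejects in about 5% of no-signal studies with 2 or 8 predictors. A permutation test of the whole fit rejects in 4-5%.
- At a true AUC of 0.7, power is about 99-100% with two predictors. With eight it is about 95-96% for tBPAR and 96-98% for infection.
- Bootstrap optimism correction brings the apparent 0.704 to about 0.695 (two predictors) and 0.725-0.728 to 0.68 (eight), close to new-data performance. With eight noise predictors it still averages 0.53-0.54, so the corrected AUC should not itself serve as the test against 0.5.

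**The case against.** **The SAP may deal with this.** Internal validation is commonly specified there, and including all participants is compatible with bootstrap or cross-validation. Nowhere does the protocol say that uncorrected performance will be reported. This stands, and it makes the inflation conditional. It does not remove the mismatch inside the protocol, where the alpha and power are printed for a score that 8.c then fits.

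**The largest figure is an extreme.** The protocol does not say that all eight summaries enter one model, and the 85% also supposes that both markers are pure noise, whereas 3.c reports earlier signal for each. With two predictors at the planning value of 0.7, the excess is only about 0.01 against a half-width of 0.081. This stands too. The no-signal error with two predictors is still about three times the nominal level.

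**The test against 0.5 is a sample-size rationale.** The primary endpoint compares accuracy with LFTs. True, but 8.c plans an AUC with a 95% interval, and 8.b says what that would be taken to show.

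A reader might also infer four stronger points, which the documents do not support:

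- *The threshold inflates the AUC.* The AUC does not depend on a cut-off.
- *The combination would be declared better than a single marker too easily.* Four noise summaries added to a real marker raise the in-sample AUC in about 96% of studies, and one does so in about 75%. But the protocol does not treat any rise as success, and the paired DeLong test favours the combination in at most about 2.6% of such studies, which is below nominal.
- *The threshold will be used in the follow-on trial.* Section 3.b mentions the trial but no threshold.
- *The study is too small.* Step 5 shows otherwise.

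**Conclusion.** The point holds in a limited form. The 5% alpha and the 99.7% / 99.9% power in 8.b are correct for a fixed score and do not describe the fitted combination in 8.c. Without correction, the no-signal error is about 15% on the most favourable reading and up to about 85% on the least. The apparent AUC is optimistic by about 0.01 to 0.05 at a true AUC of 0.7. Accuracy at the chosen cut-off is optimistic by about 0.07 on the Youden scale (0.34 − 0.27).

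These sizes assume normal predictors, independent unless stated, any signal in one predictor, complete data on 210 participants, and two to eight predictors; the protocol does not fix that number. The mixed and joint models were not simulated. The point should be put right before analysis, but it does not threaten the design.

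**What to change.** 1. In 8.c, state that the AUC is reported after bootstrap optimism correction or cross-validation that repeats every data-driven step in each resample (choice of summaries, model fit, cut-off). Correct sensitivity, specificity, PPV and NPV at the chosen threshold in the same way.
2. In 8.b, rest the claim of any ability to discriminate on a likelihood-ratio test of the logistic model against the intercept-only model, or on a permutation test of the whole fit. If summaries are selected from the data, use the permutation test with the selection repeated inside it.
3. Test the added value of the combination over a single marker with the likelihood-ratio test of the nested models. With noise added to a real marker it rejects in about 5-6% of studies.
4. Optionally, name one summary per marker in advance. This reduces the optimism but does not replace items 1 and 2, since two fitted predictors already give about 15%.

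The cost is some programming and slightly lower reported accuracy. No extra participants or samples are needed.

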9. STORAGE OF BLOOD AND TISSUE SAMPLES

a. DETAILS OF WHERE SAMPLES WILL BE STORED, AND THE TYPE OF CONSENT FOR FUTURE USE OF SAMPLES

Blood samples will be processed at the ONJCRI, Austin Health and stored in a specially allocated -80°C freezer in the LTU, Austin Health. The blood samples will be stored for seven years after study closure. After seven years, the blood samples will be disposed of in designated hazardous waste bins as per hospital/laboratory protocol.

The consent obtained will be extended in scope. This means that participants are consenting to the use of their blood samples or data in future research projects that are extensions of or closely related to this study, or in the same general area of research.

10. DATA SECURITY & HANDLING

a. DETAILS OF WHERE RECORDS WILL BE KEPT & HOW LONG WILL THEY BE STORED

The database will be stored through the electronic data management program REDCAP provided through the University of Melbourne. This will be password protected and the password will only be available to the main study investigators. 10 years following study completion the electronic database will be deleted

b. CONFIDENTIALITY AND SECURITY

Blood samples will be processed in the ONJCRI, Austin Health and stored in a specially allocated -80°C freezer in the LTU, Austin Health. The blood samples will be stored for seven years after study closure. After seven years, the blood samples will be disposed of in designated hazardous waste bins as per hospital/laboratory protocol.

Records will be kept on a secure password-locked computer in LTU, Austin Health. The database will be stored stored through the electronic data management program REDCAP provided through the University of Melbourne, on a single computer with a password that is only available to the main study investigators. The UR numbers will be recorded against patient study numbers in a separate file with a separate password on the same computer. 10 years following study completion, the records and electronic database will be deleted.

No identifiable individual information will be presented in any publication. Any papers arising from this project will provide de-identified or cohort information only.

11. **R**EFERENCES

- 1. Thurairajah PH, Carbone M, et al. Late acute liver allograft rejection; a study of its natural
- 2. history and graft survival in the current era. Transplantation. 2013 Apr 15;95(7):955–9.

